## SCHEDULE OF STUDY ASSESSMENTS

Study design and schedule of assessments. (Shaded columns represent assessments performed in-clinic, non-shaded for remote visits).

|  | Pre-Surgery | Surgery        | Discharge      | Post-Surgery Visits |         |         |         |           |           |           |   | Unscheduled visit |
|--|-------------|----------------|----------------|---------------------|---------|---------|---------|-----------|-----------|-----------|---|-------------------|
| Visit  | 1           | 2              | 3  | 4                   | 5       | 6       | 7       | 8         | 9         | 10        |   |                   |
| Day / Month  | ≤21 Days    | Day 0          | Day 0 or 1     | Day 7               | Day 14  | Month 1 | Month 3 | Month 6   | Month 9   | Month 12  |   | N/A               |
| Visit Window (Days)                                      |             |                |                | ±3                  | -3 / +6 | ±7      | ±14     | -21 / +14 | -21 / +14 | -21 / +14 |   | N/A               |
| Informed Consent   | X           |                |                |                     |         |         |         |           |           |           |   |                   |
| Inclusion/Exclusion                                      | X           |                |                |                     |         |         |         |           |           |           |   |                   |
| Pregnancy Test (if applicable)                           |             | X  |                |                     |         |         |         |           |           |           |   |                   |
| Medical History  | X           |                |                |                     |         |         |         |           |           |           |   |                   |
| Analgesics usage   | X           | X  | X              | X                   | X       | X       | X       | X         | X         | X         | X |                   |
| Demographics   | X           |                |                |                     |         |         |         |           |           |           |   |                   |
| Vital Signs (HR/BP/T/Ht/Wt)                  | X           | X  | X              |                     | X       |         | X       | X         |           |           |   | X                 |
| Randomization                                |             | X  |                |                     |         |         |         |           |           |           |   |                   |
| Hernia Information (type & size)                         | X           | X  |                |                     |         |         |         |           |           |           |   |                   |
| Use of Investigational or control device                 |             | X  |                |                     |         |         |         |           |           |           |   |                   |
| Number of Investigational or control device applications |             | X  |                |                     |         |         |         |           |           |           |   |                   |
| Photograph following mesh fixation                       |             | X              |                |                     |         |         |         |           |           |           |   |                   |
| Photograph following peritoneal closure      |             | X              |                |                     |         |         |         |           |           |           |   |                   |
| Clinician evaluation of hernia repair & PE   |             |                |                |                     | X       |         | X       | X         |           |           |   | X                 |
| Subject Pain (0-10 VAS) Assessment                       | X           |                | X              | X                   | X       | X       | X       | X         | X         | X         |   |                   |
| Subject QOL Assessment                                   | X           |                |                | X                   | X       | X       | X       | X         | X         | X         |   |                   |
| AE Evaluation  |             | X  | X              | X                   | X       | X       | X       | X         | X         | X         | X |                   |

Immediately prior to surgery

During surgery

At discharge post-surgery, either on same day as surgery or next day post-surgery according to standard of care

Height only required at Pre-surgery visit. Unless Pre-surgery (Visit 1), Surgery (Visit 2) and Discharge (Visit 3) occur on the same date, weight should be obtained for each separate visit. Vital signs may be obtained remotely at Month 3 and 6 visits as volunteered by subjects using their own devices as available (e.g. thermometer, weight scales, smart wearable technology)

Patient must be blinded to the randomized device

Photograph following peritoneal closure only required for TAPP repairs

Suspected hernia recurrence will be confirmed by ultrasound imaging following physical examination

## STATISTICAL CONSIDERATIONS

### Statistical Hypotheses

Statistical methods are presented below.

**Primary Endpoint:** Effectiveness of LiquiBand FIX8® will be assessed and compared to treatment with AbsorbaTack™ in subjects requiring laparoscopic (TEP and TAPP) hernia repair. Success will be determined by improvement in pain not inferior to control device as measured by a VAS value (0 = no pain to 10 = most pain imaginable) from baseline (worst pain experienced within 1 month of screening visit) to six months post hernia repair.

The statistical hypothesis is:

$$H_0: \delta_T - \delta_C \geq 0.9^{[21, 22]}$$

$$H_1: \delta_T - \delta_C < 0.9^{[21, 22]},$$

where  $\delta$  is the change from baseline (worst pain experienced within 1 month of screening visit) to 6-month on VAS for the appropriate treatment group.

**Secondary Endpoints:** To assess efficacy and safety outcomes following TAPP or TEP laparoscopic groin hernia (femoral and inguinal) repair by LiquiBand FIX8® compared to AbsorbaTack™ by evaluating the following:

- Recurrence rate in subjects following laparoscopic (TEP and TAPP) groin hernia repair by LiquiBand FIX8® or control (AbsorbaTack™) at 2 weeks, 3 months, 6 months, and 12 months.

The statistical hypothesis for the recurrence rate at 6 months is:

$$H_0: q_T - q_C \geq 10\%^{[25]}$$

$$H_1: q_T - q_C < 10\%^{[25]},$$

where  $q$  is the recurrence rate at 6 months for the appropriate treatment group.

- Rate of successful hernia mesh fixation in subjects undergoing TEP and TAPP laparoscopic groin hernia repair.

The statistical hypothesis is:

$$H_0: p_C - p_T \geq 10\%$$

$$H_1: p_C - p_T < 10\%,$$

where  $p$  is the rate of successful hernia mesh fixation at time of surgery for the appropriate treatment group.

- Rate of successful peritoneal closure in subjects undergoing laparoscopic TAPP hernia repair.

The statistical hypothesis is:

$$H_0: \pi_C - \pi_T \geq 15\%$$

$$H_1: \pi_C - \pi_T < 15\%,$$

where  $\pi$  is the rate of peritoneal closure at time of surgery for the appropriate treatment group.

- Quality of Life assessed by the Carolinas Comfort Scale (CCS) Questionnaire prior to surgery and at 7 days, 14 days, 1 month, 3 months, 6 months, 9 months and 12 months following laparoscopic (TEP and TAPP) groin hernia repair.

### Population for Analysis

The following subject populations will be created:

- Intent-to-Treat (ITT): All enrolled subjects. ITT analysis will be per randomized group irrespective of the treatment actually received.
- Per Protocol (PP): All ITT subjects excluding those with major protocol violations. PP analysis will be per actual treatment group which is the same as the treatment initially randomized.
- As the PP analysis is more conservative for non-inferiority hypothesis, all hypotheses will be tested with the PP population. ITT analysis will also be performed for all hypotheses, as the primary analysis for the primary endpoint, and the supportive analysis for secondary endpoints with non-inferiority hypothesis.

## Statistical Analysis

### General Approach

The primary efficacy endpoint will be tested for non-inferiority of treatment to control with a predefined non-inferiority margin of 0.9 on the VAS scale. Confounding factors for the pain score including analgesic use or other pain management therapies will be measured at screening and all follow up visits, and compared between treatment arms to ensure proper balance within each site. The study will be claimed successful if both PP and ITT analyses on the primary efficacy endpoint showed significance at 0.025. Once the hypothesis tests succeed for both analysis sets on the primary efficacy endpoint, key secondary endpoints will be compared between treatments sequentially in a non-inferiority manner. The following sequential analysis approach will be taken:

- Primary non-inferiority on the PP set; if significant at one-sided alpha=0.025, and
- Primary non-inferiority on the ITT set; if significant at one-sided alpha=0.025, then proceed to key secondary endpoints detailed in Section 3.1.
- Secondary non-inferiority on the PP set on Hernia Recurrence rate in subjects following laparoscopic (TEP and TAPP) groin hernia repair by LiquiBand FIX8® or control (AbsorbaTack™) at 6 months, at one-sided alpha=0.025.
- Secondary non-inferiority on the PP set on Rate of successful hernia mesh fixation in subjects undergoing TEP and TAPP laparoscopic groin hernia repair; if significant at one-sided alpha=0.025, then
- Secondary non-inferiority on the PP set on Rate of successful peritoneal closure in subjects undergoing laparoscopic TAPP hernia repair; if significant at one-sided alpha=0.025, then

The family-wise type I error will therefore be controlled at 0.025.

Summary statistics will consist of the number and percentage of responses in each category for discrete variables, and the mean, median, standard deviation (SD), minimum, and maximum for continuous variables. One-sided statistical tests will use a significance level of  $\alpha = 0.025$ , and two-sided tests will use a significance level of  $\alpha = 0.05$ .

### Analysis of the Primary Efficacy Endpoint

To test change from baseline (worst pain experienced within 1 month of screening visit) to 6-month on VAS between LiquiBand FIX8® and AbsorbaTack™, a general linear model (ANCOVA) will be run using SAS Proc GLM, with the treatment arm and laparoscopic repair technique (TAPP or TEP) as covariates. (SAS Institute Inc. NC USA). A p-value of  $< 0.025$  will be considered evidence that LiquiBand FIX8® is not inferior to the AbsorbaTack™. 95% confidence interval will be calculated for the difference on changes from baseline (screening visit) to 6-month visit on VAS between LiquiBand FIX8® and AbsorbaTack™. This endpoint will be assessed when the enrollment is completed, i.e., when 148 subjects have been enrolled in the TAPP cohort, and there are at least 226 evaluable subjects with 6-

month data for change from baseline to 6-month on VAS. Tipping point analysis will also be performed to evaluate the impact of missing data.

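### As written, the decisive ITT test states no handling of a missing Month-6 VAS and, by inference, becomes a completers' test that leaves the earlier VAS unused

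*Combined protocol and SAP*

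**What the plan says.** - **Analysis set.** Population for Analysis defines "Intent-to-Treat (ITT): All enrolled subjects", analysed as randomized. The same section adds "ITT analysis will also be performed for all hypotheses, as the primary analysis for the primary endpoint".
- **Success rule.** General Approach: "The study will be claimed successful if both PP and ITT analyses on the primary efficacy endpoint showed significance at 0.025". No other condition is attached to the primary claim.
- **Model.** Analysis of the Primary Efficacy Endpoint: "a general linear model (ANCOVA) will be run using SAS Proc GLM". The response is one change score per subject, and the terms are treatment arm and repair technique. Neither an imputation step nor a repeated-measures model is described.
- **Missing data.** One sentence in the same section: "Tipping point analysis will also be performed to evaluate the impact of missing data". It gives no base-case handling and no range of shifts.
- **Timing.** The endpoint is assessed "when 148 subjects have been enrolled in the TAPP cohort, and there are at least 226 evaluable subjects" with Month-6 data. The Clinical Investigation Summary plans 284 subjects, 142 per arm.
- **Data at hand.** In the Schedule of Study Assessments, the row "Subject Pain (0-10 VAS) Assessment" is ticked at pre-surgery, discharge, Days 7 and 14, and Months 1, 3, 6, 9 and 12. Footnote 5 there reads "Patient must be blinded to the randomized device".

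**The concern.** The test that decides the trial is labelled as covering every enrolled subject, yet nothing says how a subject without a Month-6 VAS enters it. Proc GLM leaves out any record with a missing response, so without a prior imputation step the ITT test is run on completers. This is an inference from the software default and not a statement in the plan, but the wording about evaluable subjects with Month-6 data fits it.

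Pain is both the outcome and a plausible reason for leaving follow-up. If subjects doing badly leave the LiquiBand arm more often than the control arm, the remaining LiquiBand subjects look better than the full arm, and the observed difference moves away from the 0.9 margin in the direction that favours the claim. Scores from discharge to Month 3 could correct much of this, but the stated model cannot use them.

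**Working it through.** **Inputs from the documents.** 142 per arm; margin 0.9 VAS points; one-sided 0.025; at least 226 evaluable. Largest shortfall at the trigger: (284 − 226)/284 = 58/284 = 20.4%.

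**Inputs assumed.** The text gives no SD, power or dropout rate, so 284 and 226 cannot be derived from stated inputs. Two things fit. First, 113/(1 − 0.20) = 141.25, which rounds up to 142 per arm. Second, 113 per arm has 80% power at a true difference of 0 when SD = 0.9 × √(113/2)/(1.96 + 0.84) ≈ 2.4. I take SD 2.4, a Month-3 to Month-6 correlation of 0.5 to 0.7, and equal loss per arm of 10% or 20.4%.

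**Step 1, size of the effect by formula.** Let s be the extra LiquiBand-minus-control difference among lost subjects relative to completers. If the true all-enrolled difference is exactly 0.9, the completers' difference is 0.9 − 0.204s, and

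P(false non-inferiority) = Φ(0.204s/SE − 1.96), SE = SD × √(2/113).

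At SD 2.415, SE = 0.321, and s = 1 gives Φ(0.635 − 1.96) = 9.3%. At SD 2.087 (the value for 90% power) it gives 11.0%. At s = 0 it is 2.5%. So everything turns on whether lost subjects differ *between arms*.

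**Step 2, simulation of the mechanism.** 142 per arm, true difference 0.9, loss weight exp(k × z-score of Month-3 VAS), 20 imputations by arm, 4000 runs. The two figures in each cell are for correlation 0.5 and 0.7.

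| Loss tied to Month-3 pain | Completers, 10% | Completers, 20.4% | Imputation, 10% | Imputation, 20.4% |
|---|---|---|---|---|
| Equal in both arms | 2.9%, 2.8% | 2.7%, 2.8% | 2.6%, 2.6% | 2.4%, 1.8% |
| Both arms, k twice as large in LiquiBand | 3.3%, 4.4% | 4.5%, 7.3% | 2.4%, 2.3% | 1.8%, 2.3% |
| LiquiBand only | 6.2%, 7.3% | 11.6%, 19.7% | 2.8%, 2.4% | 2.7%, 3.0% |
| Control only | 0.7%, 0.8% | 0.3%, 0.2% | 2.3%, 2.7% | 2.2%, 2.6% |

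Hand check of one cell: LiquiBand only, 10% loss, correlation 0.5 has bias −0.127. SE = 2.4 × √(2/127.8) = 0.300, and Φ(0.127/0.300 − 1.96) = 6.2%, as in the table.

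The Monte Carlo standard error is about 0.3 points at rates of 2.5% to 5%. Repeat runs moved single cells by about one point, and one purely random-loss cell printed 1.7% where theory gives 2.5%. The rates are therefore quoted as rough ranges. For LiquiBand-only loss at correlation 0.6, SDs of 2.0, 2.4 and 2.8 give 7.3%, 6.7% and 6.8% at 10% loss, so the assumed SD matters little.

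**Step 3, what imputation does not repair.** If LiquiBand loss depends on the unseen Month-6 score itself, completers give 12% to 13% (10% loss) and 34% (20.4%). Imputation still leaves 7% to 9% and 15% to 23%.

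**Step 4, how far the tipping point lies.** Shift in the lost LiquiBand subjects at which non-inferiority fails:

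(0.9 − estimate − 1.96 × 2.4 × √(2/(142 × (1 − loss))))/loss

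- Estimate 0: (0.9 − 0.588)/0.10 = 3.1 points; (0.9 − 0.626)/0.204 = 1.3 points.
- Estimate 0.2: (0.7 − 0.588)/0.10 = 1.1 points; (0.7 − 0.626)/0.204 = 0.4 points.

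With little loss and no observed difference the claim is robust. With more loss and a small observed difference, a modest shift overturns it.

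**The case against.** **The text may be incomplete.** General Approach refers to a Section 3.1 that cannot be identified here, and the hypotheses cite references 21, 22 and 25 while the visible list ends at 9. A missing-data rule may exist elsewhere. This stands as a limit on the point: if there is such a rule, a cross-reference settles it.

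**Missing data are not ignored.** A reader might infer that they are. That is wrong, because a tipping-point analysis is planned. It does not, however, alter the test that decides success, and it needs a base-case value for each missing score, which is not stated. A reader might also infer that its result must enter the success rule. Keeping a sensitivity analysis outside that rule is ordinary practice, so this would be a preference and not a correction.

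**Nothing shows that loss will differ by arm.** Subjects are blinded, so similar loss is the reasonable base case, with practically no inflation. This stands. The documents do not support a reading that the trial's error rate *is* inflated.

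**20.4% is not an expected dropout rate.** It comes from a minimum trigger, and part of the shortfall may be subjects who have not yet reached Month 6, whose absence is unrelated to pain. This also stands: if half is administrative, the one-arm worst case falls to about 6% to 9%.

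**Imputation is a partial cure.** True (Step 3). It covers loss explained by recorded scores; the tipping-point analysis covers the rest.

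**Conclusion.** The point holds as a conditional weakness in the decisive test. Run as the visible text describes, the ITT analysis is a completers' analysis and discards scores that the trial already collects. Its size depends on the loss pattern:

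- similar loss in both arms: about 2% to 3.5%, practically nominal;
- greater pain-related loss with LiquiBand: roughly 5% to 7% at 10% loss in the one-arm worst case, with 10% to 20% at 20.4% as an upper bound;
- greater pain-related loss with control: below 1% when confined to that arm, so conservative.

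These figures rest on an assumed SD of 2.4, a correlation of 0.5 to 0.7 and equal loss per arm, and the simulation did not model the bounds of the 0 to 10 scale. The omission of subjects is inferred from a software default. The change should be made because it is cheap and removes an avoidable dependence on equal loss, not because a bias has been shown. Confidence is medium.

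**What to change.** State in the SAP how a missing Month-6 VAS enters the ITT primary test. Run that test on every subject in the ITT set as the plan defines it. Use multiple imputation by arm from baseline VAS, repair technique and VAS at the other visits, followed by the stated ANCOVA. An equivalent likelihood-based repeated-measures model would also serve.

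Use the same analysis as the base case of the tipping-point analysis and state its arm-specific shifts in advance. It may remain a sensitivity analysis outside the formal success rule; its task is loss that depends on the unseen Month-6 value.

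**Cost.** SAP wording and modest programming. No new data are needed, since the VAS visits are already scheduled. At a true difference of 0, simulated power (3000 runs) with imputation minus completers ranged from −0.2 points (0.849 − 0.851) to +4.1 (0.837 − 0.796) under random loss. Under equal pain-related loss it ranged from −2.3 (0.789 − 0.812) to +0.5 (0.830 − 0.825).

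### The primary model is called ANCOVA but omits baseline VAS: the non-inferiority test is valid, yet less precise than the collected data would allow at almost no cost

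*Combined protocol and SAP*

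**What the plan says.** Under Analysis of the Primary Efficacy Endpoint, "a general linear model (ANCOVA) will be run using SAS Proc GLM", "with the treatment arm and laparoscopic repair technique (TAPP or TEP) as covariates". The outcome is defined under Statistical Hypotheses, where δ "is the change from baseline (worst pain experienced within 1 month of screening visit) to 6-month on VAS for the appropriate treatment group". General Approach sets a "predefined non-inferiority margin of 0.9 on the VAS scale" and the success rule: "The study will be claimed successful if both PP and ITT analyses on the primary efficacy endpoint showed significance at 0.025". The analysis is triggered when enrollment is complete and "there are at least 226 evaluable subjects" have 6-month data.

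The Schedule of Study Assessments has the row "Subject Pain (0-10 VAS) Assessment" marked at the pre-surgery visit, and randomization takes place during surgery. Baseline VAS is therefore a pre-randomization measurement. General Approach also says that analgesic use and other pain therapies will be compared between arms. That is a balance check; it does not put baseline pain into the model.

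**The concern.** An analysis of covariance on a change score normally carries the baseline value as a continuous covariate. Here the label is present and the covariate is not.

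Subtracting baseline is not the same as adjusting for it. The change score fixes the slope of 6-month VAS on baseline at 1, whereas adjustment estimates that slope. When the true slope is below 1, subtraction over-corrects. It adds baseline noise to the outcome and carries chance baseline imbalance between the arms into the estimate, which widens the interval that is compared with 0.9.

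That interval has to clear the margin in both the PP and the ITT set, and the key secondary tests are reached only if it does. The stake is power. Bias and type I error are not in question.

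**Working it through.** **Inputs from the documents.** Margin 0.9, one-sided alpha 0.025, planned N 284 (142 per arm), at least 226 evaluable (113 per arm if split equally).

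**Inputs not in the documents.** The SD of VAS at either time, the correlation ρ between baseline and 6 months, the intended power and the expected loss. The plan's sample size therefore cannot be reproduced from its own inputs. Back-solving, 113 per arm with true difference 0 gives 80% power if the SD of change is about 2.40. A 20% loss would link 226 to 284, since 113/0.80 = 141.25, rounded up to 142 per arm. Both figures are inferences.

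**Formulas.** Let s_b and s_6 be the SDs at baseline and 6 months.
- Change-score variance: s_b² + s_6² − 2ρ·s_b·s_6
- Baseline-adjusted variance: s_6²(1 − ρ²)
- Slope of 6-month on baseline VAS: ρ·s_6/s_b
- With equal SDs, the ratio of the first variance to the second is 2/(1 + ρ).

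Power is from the noncentral t distribution with standard error SD·√(2/113) and true difference 0, on 223 df unadjusted and 222 adjusted.

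**Equal SDs of 2.5, 113 per arm.** The last column is the adjusted sample size carrying the same information as 226 on change scores, 226/ratio.

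| ρ | Variance ratio | Power unadjusted | Power adjusted | Equivalent adjusted N |
|---|---|---|---|---|
| 0.2 | 1.67 | 57% | 79% | 136 |
| 0.3 | 1.54 | 62% | 81% | 147 |
| 0.4 | 1.43 | 69% | 84% | 158 |
| 0.5 | 1.33 | 77% | 88% | 170 |
| 0.6 | 1.25 | 85% | 92% | 181 |

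At ρ = 0.3 the change SD is √8.75 = 2.958 and the adjusted SD is √5.6875 = 2.385. The 95% CI half-widths are 1.97 × 2.958 × √(2/113) = 0.78 and 1.97 × 2.385 × √(2/113) = 0.63.

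**Anchored to 80% power for the planned model** (change SD 2.40, equal SDs). Adjusted power is 95%, 94%, 92%, 90% and 88% for ρ = 0.2 to 0.6. This version needs no assumption about the absolute SD beyond the 80% itself.

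**Unequal SDs.**
- Less spread at 6 months (2.5 then 1.5): the ratio is 7.00/2.16 = 3.24 at ρ = 0.2 and 4.00/1.44 = 2.78 at ρ = 0.6.
- More spread at 6 months (2.0 then 2.5): the ratio is 8.25/6.00 = 1.38 at ρ = 0.2 and 4.25/4.00 = 1.06 at ρ = 0.6. At ρ = 0.8 it is 2.25/2.25 = 1.00, where the slope is 0.8 × 2.5/2.0 = 1.

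**Validity, by simulation** (N = 226, change SD 2.4, equal SDs, ρ = 0.3). With the true difference at the margin, the rejection rate was 0.025 without baseline and 0.024 with it. At true difference 0, power was 0.80 and 0.94. Conditional on the LiquiBand arm's baseline being more than one standard error higher, the unadjusted test at the margin rejected about 10% of the time; when it was more than one standard error lower, about 0.1%. With baseline in the model these rates were 2.7% and 2.4%. This conditional swing is already inside the change-score standard error and is not a second loss to be added to the first.

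**The case against.** Nothing in the planned test is wrong: it is unbiased, holds its level, and the documents do not show that power is inadequate. That is correct and limits the point to an efficiency gain.

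The size also rests on no figure in the documents, and normal-theory power for a bounded 0-10 scale should not be read too finely. If 6-month VAS varies more than baseline and the correlation is high, the gain is small: with SDs 2.0 and 2.5 and ρ = 0.6, power goes from 90.4% to 92.0%, and at slope 1 nothing is gained. This stands. The documents do not exclude that case, although a slope of 1 would be unusual between worst pain before repair and pain six months after it.

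The evaluable number is a minimum. With all 142 per arm, the case of SD 2.5 and ρ = 0.3 becomes 72% against 89%, in place of 62% against 81%. The lower absolute powers should therefore not be read as a forecast of underpowering.

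Finally, the ANCOVA label may mean that baseline was intended and dropped from the list. The text cannot settle this. Either way the model statement needs to be made explicit.

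**Conclusion.** The point holds as a recommended improvement. The primary model as written omits baseline VAS, and no section supplies it. The direction of the effect is secure: apart from the one degree of freedom, adjustment does not lose precision in a sample of this size, and it gains whenever the slope differs from 1. The amount is uncertain. Under equal SDs and correlations of 0.2 to 0.6, the planned analysis gives up 20% to 40% of the information available (1 − 1/1.25 to 1 − 1/1.67). The loss is larger if pain varies less at six months than at baseline, and smaller if it varies more. Neither a validity failure nor a demonstrated shortage of power is claimed.

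**What to change.** In Analysis of the Primary Efficacy Endpoint, add baseline VAS, the same value used to form the change score, as a continuous covariate alongside treatment arm and repair technique. State that the model applies to both the PP and the ITT analysis. Take the treatment difference and its 95% confidence interval from that model and compare it with the unchanged 0.9 margin at the unchanged alpha. The tipping point analysis named in the same section should use the same model, so that it examines the primary result itself. Make the change before any unblinded outcome data are seen.

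The cost is a sentence or two of text and one degree of freedom (the critical t moves from 1.97066 to 1.97071). No new data are needed and no subject is lost, because a change score cannot be formed without the baseline value. The treatment difference being estimated stays the same. If the sponsor prefers to leave baseline out, the plan should give the reason and stop calling the model an ANCOVA.
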